Abstinence at 4 weeks post TQD is defined as a self-report of no smoking of conventional cigarettes (not a puff) for the previous 2 weeks, validated by a CO reading of <8ppm. Participants who do not provide a CO reading at Week 4 will be considered to be smoking at 4 weeks. 24 and 52 week sustained abstinence will be calculated in accordance with the Russell Standard [6] as a self-report of smoking no more than 5 cigarettes since 2 weeks post TQD, validated by CO readings of <8ppm at the 52 week follow up. Participants lost to follow up or not providing biochemical validation will be included as non-abstainers.

Study methods

Overall study design and plan

Target for randomisation:	886
Date of first randomisation:	11.05.2015
Date of last randomisation:	01.02.2017
Trial design:	Individually randomised, parallel group
Who is blinded:	Participants and researchers are blinded up until the point of randomization.
Randomised Interventions:	Intervention (EC) vs. control (NRT)
Allocation ratio:	1:1

Study population

The study population consisted of people responding to advertising (typically posters, leaflets, digital media, local papers, on local transport, through GP practices, mail outs to previous attendees, and in local radio/newspaper interviews).

Participants were eligible to take part if they were age 18 years and older, a current smoker accessing a stop smoking service (SSS) and able to read/write/understand English.

Participants were excluded from participating if they were pregnant or breastfeeding, had a strong preference to use or not to use NRT or EC in their quit attempt, were enrolled in other interventional research, or currently using NRT or EC.

Method of treatment assignment and randomisation

Randomisation (1:1 in permuted blocks) was undertaken using a web-based application, set up by the Barts Clinical Trials Unit (Barts CTU), and was stratified by study site. Participants who were eligible and consent to take part were randomly allocated to the experimental or control interventions at the target quit day (TQD) session. The TQD was used as the point of randomisation to limit any differential drop-out. The staff randomising the patient accessed the web-based application when the participant was with them, entering their participant ID number, date of birth and initials into the program. There were no stratification factors within study sites. The allocation was immediately provided by the program.

Treatment masking (Blinding)

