Participants could not be blinded to the intervention they were receiving and study staff could not be blinded when providing the interventions. However, collective unblinded data were only seen and analysed for the purposes of the DMECs by the trial statistician. The trial statistician was not involved in the decisions about the analysis and the treatment of deviations after randomisation (e.g. protocol violations, losses to follow up, withdrawals from the study).

All other trial staff who have access to outcome data remained blinded until data analysis was complete. Final data analysis will be conducted blind to treatment allocation.

Sample size determination

The 12-month validated abstinence rate (Primary outcome) associated with UC in our setting was initially assumed to be 14% [7]. Our projection of a feasible rate with the EC is based on our work and two published studies. Our work^[8] suggests that EC delivers nicotine quickly, with Tmax occurring within 5 minutes. This is similar to nicotine nasal spray. In a comparative study of the nasal spray + patch versus patch alone in Iceland, 1-year abstinence rates were 27% vs. 11%, Risk Ratio (RR) = 2.45 [9]. More relevant, in a recent cohort study in Italy, a second generation EC achieved 36% CO validated abstinence at 6-months [10]. Assuming 25% relapse between 6 and 12 months [11], this would translate to a 1-year rate of 27%. Relative to our assumed UC rate, this would give RR = 1.9. However, quit rates in countries with little tradition of stop-smoking treatments tend to be much higher than in the UK.

We wish to detect a RR of 1.7 (EC rate = 24%) with 0.95 power, but also have reasonable power (say, 0.75) if the RR should be as low as 1.5 (EC rate = 21%). This latter figure would still represent a clinically significant difference. To achieve these levels of power (2-sided, alpha = 0.05, continuity correction), a total of 886 participants (443 in each group) are required.

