Notes: Since the study protocol was written, a new evaluation of the UK stop smoking services was published [12]. The validated one-year quit rate has declined to 8%. This comprised general practice and pharmacy services with quit rates of 5% and specialist support with quit rates of 10% for individual and 12% for group support. The decline is probably due to a 'hardening' of treatment population, e.g. the services see an increasing number of re-attenders, people with serious health issues etc. Using a quit rate of 10% in the UC arm that provides multi-contact support, and 17% in the EC arm (RR=1.70) the study sample size still provides 86% power to detect such a difference with a two-tail test of proportions.

Assuming the true percentage in both arms is 10%, the 95% confidence interval for the difference in proportions will have width of +/-4% around the observed difference.

If the difference in proportions is non-significant, we will undertake a non-inferiority analysis, using a two-sided confidence interval of the difference in the abstinence percentages between the two arms. Assuming that the true percentages are 10% in the control arm and 12% in the intervention arm, our sample size of 886 will provide 88% power to exclude a difference in favour of the standard group of 4% or more.

Data collection

Baseline

The following variables were collected at baseline:

- **Demographics:** includes age, sex, marital status, ethnicity, employment, level of education, eligibility for free prescriptions,
- **Smoking measures:** Fagerstrom Test for Cigarette Dependence (FTCD) [13], previous stop smoking product use, age first started smoking and whether partner/spouse smokes. Mood and Physical Symptoms Scale (MPSS) [14], carbon monoxide reading
- **Current Health and Medications**
- **Health problems checklist**

The following validated questionnaires are also administered at baseline:

- EQ-5D
- Smoking Cessation and Health Service Use Questionnaire

Follow up

The following variables were collected during follow-up visits:

- Current smoking behaviour
- Mood and Physical Symptoms Scale (MPSS) – 1 and 4 weeks post quit only
- Carbon monoxide reading
- Allocated product use, helpfulness, taste and satisfaction ratings (1 and 4 weeks post quit only), purchase and reasons for stopping (where applicable)
- Non-allocated product use and purchase
- Current health and medications
- Health problems checklist

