The following validated questionnaires are also administered at 6 and 12 month follow up:

- EQ-5D
- Smoking Cessation and Health Service Use Questionnaire

Timing of data collection

The recruitment period was: 11 May 2015 – 01 February 2017 (22 months) and the study sessions were conducted as follows:

Week -1	Baseline
Week 0:	Randomisation (TQD)
Weeks 1-4:	Treatment sessions, 1, 2, 3 and 4 weeks post TQD (Q+1, Q+2, Q+3 and Q+4)
Month 6:	Follow-up, 24 weeks post TQD (Q+24)
Month 12:	Follow-up, 52 weeks post TQD (Q+52)

Database

Description

Data were entered into the online database, 'Oracle Database 11g', hosted at the Barts Cancer Centre. The Electronic Data Capture forms are web based and built using Java with data validation in JavaScript (Java framework Struts 2).

Data quality

The study team check the data for discrepancies each week, and clarify any potential data entry errors with the relevant advisor/researcher or participant. When recruitment and follow-up are complete, the study team will clean the data in the following way: values for each variable will be sorted, and those at the extremes will be checked to ensure that they are within the expected range.

Source data verification will also be conducted where paper CRFs have been used: a random sample of 10% of CRFs will be selected, and the study team will compare all written entries with those entered onto the main study database. The pre-specified data quality target is $\leq 2\%$ discrepancy rate between entries in the CRF and the electronic database. If an error is found in $>2\%$ of entries, the quality target for data entry will not have been met, and all CRF data will be cross-checked against data in the study database.

Derived and computed variables

All derived and computed variables will be documented in the analysis programmes.

General issues for statistical analysis

General analysis principles

The main analysis for each outcome will use intention-to-treat (ITT) principles, meaning that all participants with a recorded outcome will be included in the analysis, and will be analysed according to the treatment group to which they were randomised. More information on which participants will be included in each analysis is available in the section below. All p-values will be two sided, and the significance level is set at 5%.

Analyses for all outcomes will be presented as:

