- The number of participants included in the analysis, by treatment group. NB. for the primary outcome data this will be all randomised participants – see missing data section below);
- A summary measure of the outcome, by treatment group (e.g. mean (SD) for continuous outcomes, number (%) for binary outcomes);
- A treatment effect (risk ratio of abstinence for EC relative to NRT), with a 95% confidence interval;
- A two-sided p-value.

Missing data for outcomes

To deal with incomplete data (i.e. when patients have missing data at one of the follow-up time points) we will:

- Attempt to follow up all randomised patients even if they discontinue participation.
- Include participants lost to follow-up (missing cases) or not providing biochemical validation as non-abstainers.
- Carry out a sensitivity analysis using different assumptions about missing cases (e.g. using the Hedeker method [15] and last known quit status), as well as analyses excluding cases with missing outcomes. NB. Where a participant misses 52 week follow up, but it is already known from their 3, 4 and/or 24 week follow up that they have smoked more than 5 cigarettes since 2 weeks post TQD, they will be counted as smokers for the primary outcome in sensitivity analyses.

Withdrawn participants

Withdrawn participants (i.e. no further follow up permitted) will be included in the analysis as per intention to treat (counted as smokers for the time points after withdrawal, as per Russell Standard).

Participants who died will be excluded from the sample as per the Russell Standard.

Participants who have moved to an untraceable address (documented by returned letters) and whose telephone numbers and email address are no longer in use will be excluded from the sample from the point that notification was received that they were no longer living at the address and their telephone numbers/email address are no longer in use, as per the Russell Standard. They will be included in the sample analysis up until this point.

Analysis of primary outcome

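### The 88% power quoted for the fallback non-inferiority analysis matches a 90% confidence interval that the SAP never states; under the SAP's own two-sided 5% and 95% convention it is about 81%

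*SAP*

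**What the plan says.** The Notes under Sample size determination plan a non-inferiority analysis if the difference in proportions is not significant. It is to use a two-sided confidence interval for the difference in abstinence percentages, and the confidence level is not given. The scenario is: "Assuming that the true percentages are 10% in the control arm and 12% in the intervention arm". The claim is that "our sample size of 886 will provide 88% power to exclude a difference in favour of the standard group of 4% or more", so the margin is 4 percentage points on the absolute scale. The group size comes from the main calculation in the same section: "a total of 886 participants (443 in each group) are required".

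Wherever the SAP does state a level, it is the same one:

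- Sample size determination, main calculation: two-sided, alpha 0.05.
- The Notes, in the paragraph just before the non-inferiority plan, for the same absolute difference with both arms at 10%: "the 95% confidence interval for the difference in proportions will have width of +/-4% around the observed difference".
- General analysis principles: "All p-values will be two sided, and the significance level is set at 5" per cent.
- The list of what each analysis will present, in the same section: "A treatment effect (risk ratio of abstinence for EC relative to NRT), with a 95% confidence interval".

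No 90% interval and no one-sided 5% test appears in the document.

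**The concern.** A reader who carries the SAP's 5% and 95% convention into the non-inferiority sentence cannot reproduce the 88%. A reader who works back from the 88% arrives at a 90% interval, which the SAP does not mention. The text therefore leaves the deciding level open, and its one clue points away from everything else the document says about error rates.

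This analysis is the route by which a non-significant trial could still reach a favourable conclusion. A 95% interval tests against the margin at one-sided 2.5%; a 90% interval tests at one-sided 5%. Moving from one to the other doubles the nominal rate of false non-inferiority claims. With the level unwritten, either choice could later be presented as the plan.

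**Working it through.** **Inputs.** n = 443 per arm; control rate 0.10; e-cigarette rate 0.12; margin 0.04 (all from Sample size determination and its Notes). No allowance for drop-out is needed, because participants lost to follow-up count as non-abstainers.

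**Formula.** Non-inferiority is shown when the lower limit of the interval for (EC − NRT) lies above −0.04. With unpooled variance,

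power = Φ[(0.12 − 0.10 + 0.04)/SE − z], where SE = √[(0.10×0.90 + 0.12×0.88)/443].

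SE = √(0.1956/443) = 0.02101, and 0.06/0.02101 = 2.855.

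**Reproducing the SAP's figure.** With a 90% interval, z = 1.645: 2.855 − 1.645 = 1.210, and Φ(1.210) = 0.887. This agrees with 88% apart from rounding.

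**Under the SAP's stated convention.** With a 95% interval, z = 1.960: 2.855 − 1.960 = 0.895, and Φ(0.895) = 0.815.

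**Does the choice of method explain the gap?**

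| Method | 95% interval | 90% interval |
|---|---|---|
| Unpooled normal | 81.5% | 88.7% |
| Pooled variance | 81.4% | 88.7% |
| Farrington-Manning | 80.6% | 88.2% |
| Continuity correction | 78.5% | 86.5% |
| Exact enumeration, Wald limits | 81.7% | 88.8% |
| Exact enumeration, Newcombe limits | 81.2% | 88.7% |
| Shortcut: 10% variance in both arms | 84.5% | 90.9% |

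No 95% variant comes within 3 points of 88%. Reading 886 as the number per arm gives 98.1%, which does not explain it either. A margin of 4.5 points would give 87.1% at the 95% level, but the SAP's margin is 4. With the inputs as stated, the confidence level is what accounts for the difference.

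**Neighbouring figures.** Superiority at 10% versus 17% with 443 per arm at two-sided 5% gives 86.3% (SAP: 86%). The 95% half-width with both arms at 10% is 1.96 × √(2×0.09/443) = 0.0395, or 3.95 points (SAP: 4). Both follow the two-sided 5% and 95% convention; the 88% does not.

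**Consequence for the error rate.** With true rates exactly at the margin (control 14%, e-cigarette 10%), exact enumeration with Wald limits gives a false non-inferiority rate of 2.6% with a 95% interval and 5.1% with a 90% interval.

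**Sensitivity only.** If both arms are truly at 10%, SE = √(0.18/443) = 0.02016 and 0.04/0.02016 − 1.960 = 0.024, so power is 51% with a 95% interval. With a 90% interval it is 63%.

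**The case against.** The strongest reply is that the non-inferiority sentence gives no level, so nothing proves that the authors miscalculated. They may have worked correctly with a 90% interval and omitted to say so. Part of the evidence for 95% is also indirect: the 95% interval in the presentation list is for the risk ratio, the 5% level is stated for p-values, and the 95% interval in the preceding paragraph belongs to a precision statement. This stands to the extent that 95% is an inference, though a strong one, and that an explicit 90% interval would also be coherent. It does not rescue the present text. On that reading the deciding level is unwritten and departs from the only convention the document states.

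A second reply is that recruitment had closed (last randomisation 01.02.2017, SAP dated 08.01.2018), so a power figure for a fallback analysis can change neither the sample nor the primary chi-squared test. That is right, and it limits the weight of the point. It does not remove the need to fix the level, which bears on a possible conclusion.

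Two stronger readings are tempting. A reader might take the 51% power at equal rates as a second error. It is not: the SAP openly assumes 10% versus 12%, and its preceding paragraph already shows a half-width about equal to the margin. A reader might also infer an intention to choose the interval after seeing the result. Nothing supports that; the SAP says the final analysis is done blind to allocation. The fair statement is only that the wording permits either level.

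**Conclusion.** The point holds as an unstated confidence level combined with a power figure that does not fit the SAP's stated convention. With 443 per arm, 10% versus 12% and a 4-point margin, power is about 81% with a 95% interval, some 7 points below the quoted 88%. The quoted figure corresponds to a 90% interval (88.7%). This rests on reading the unlabelled interval as 95%, in line with every level the SAP does state, and on the full 443 per arm. The SAP excludes deaths and untraceable movers from the sample, so the analysed numbers could be slightly smaller and the power slightly lower.

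The documents do not support calling the 88% a proven arithmetic slip, because a 90% interval may have been intended. The point should be corrected before unblinding. It does not threaten the primary analysis or any estimate.

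**What to change.** In the Notes under Sample size determination, name the interval for the non-inferiority analysis as a two-sided 95% confidence interval and restate the power as about 81% for 10% versus 12%. If a 90% interval was intended, write that level explicitly, justify it as a one-sided 5% criterion, acknowledge a false non-inferiority rate of about 5% rather than 2.5%, and quote about 88-89%. Either way, settle the level before unblinding. The 51% at equal 10% rates (95% interval) may be added as a sensitivity figure, but this is optional.

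The cost is one sentence of SAP wording. Recruitment, data collection and the primary analysis do not change. Under the 95% option, the stated power becomes less favourable.

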For the primary analysis the proportion of people remaining abstinent at a year will be compared between the study arms using Chi-squared test. The treatment effect will be the risk ratio of abstinence rates for EC relative to NRT. A secondary binomial regression with log link will also be employed, which will allow for a comparison of the two study arms after adjusting for baseline variables identified as significant using a stepwise selection procedure. The analysis will be stratified by the randomization stratification factor, site; this will be done by adjusting the model using a dummy variable for site.

Sensitivity analyses for primary outcome:

A sensitivity analysis will be conducted with only participants who attended at least one treatment session, i.e. who engaged in treatment, included.

Forty two participants received a different EC device due to discontinuation of the original supply. A sensitivity analysis will be conducted with only these participants included.

To deal with participants who switched study products or used the unassigned study product for at least five consecutive days we will include them in the primary analysis in the groups to which they were randomized, but will also conduct a sensitivity analysis where they will be excluded.

Analysis of secondary outcomes

Smoking cessation and reduction outcomes

For the secondary analyses, we will examine the differences between study arms in the proportions of participants with sustained abstinence from 6 to 12 months, and at 4, 24 and 52 week follow-up,

and sustaining a 50% or greater reduction in baseline cigarette consumption and CO levels at 52 weeks, using Chi-squared test/binomial regression.

Sensitivity analyses for secondary outcomes:

Forty two participants received a different EC device due to discontinuation of the original supply. A sensitivity analysis will be conducted with only these participants included.

We will also examine time to relapse in a secondary analysis using a Cox analysis.

Definitions of smoking cessation and reduction outcomes

Primary outcome:

52 week sustained abstinence will be calculated in accordance with the Russell Standard as a self-report of smoking no more than 5 cigarettes since 2 weeks post TQD, validated by a CO reading of <8ppm at the 52 week follow up.

The following rules will apply to the primary outcome:

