As the primary outcome will be 12-month sustained, biochemically validated abstinence, a cost-effectiveness analysis will be performed at this time point. The costs will include intervention cost, smoking cessation services cost after intervention period and health resources use cost that has occurred during the 12-month period. The difference in costs between arms will be controlled for health resources use at baseline, age, sex, study site, entitlement of free prescriptions, ethnicity and baseline FTCD. The quality adjusted life years (QALYs) will be calculated during the same time period. The difference in QALYs between arms will be controlled for utility value at baseline, age, sex, study site, entitlement of free prescriptions, ethnicity and baseline FTCD. Combining both, an incremental cost-effectiveness ratio (ICER) of cost per QALY will be calculated to assess the cost-effectiveness of the intervention, comparing with the standard care. The ICER will then be compared with the national willingness-to-pay threshold of £20,000-£30,000 per QALY gained [16].

Uncertainty assessment

The uncertainty around the decision to adopt the intervention will be assessed through a non-parametric bootstrap re-sampling technique. Bootstrapping has been proposed as an efficient approach for calculating the confidence limits for the ICER as its validity does not depend on any specific form of underlying distribution [23-26]. A cost effectiveness acceptability curve (CEAC) will be plotted based on the outcomes of the 5000 bootstrap iterations [27].

A separate sensitivity analysis will be carried out to examine the impact of the assumption of LOR equating dispense on the intervention costs. This will be undertaken by using the actual quantities used reported by the participants as the cost base of the NRT costs. A set of weighted average cost per unit of the NRT products will be extracted from Prescription Cost Analysis [17] with the same approach as in the base case analysis. These unit costs will then be multiplied by the quantities reported of corresponding NRT products.

Given that the current practice for smoking cessation does not provide prescription of EC while allows prescription of pharmacotherapies, a separate analysis will be carried out, including participants' out-of-pocket money for EC and pharmacotherapies, to examine the possible cost-shift from NHS to smokers.

Handling missing data

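### The primary chi-squared test leaves out site, the only randomisation stratum, and the adjusted abstinence model takes its other covariates from stepwise selection; the cost is modest and both are easily fixed

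*SAP*

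**What the plan says.** **Randomisation.** Under Method of treatment assignment and randomisation, the SAP says that allocation in permuted blocks "was stratified by study site", and adds: "There were no stratification factors within study sites". Site is therefore the only stratum.

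**Primary test.** Under Analysis of primary outcome, "the proportion of people remaining abstinent at a year will be compared between the study arms using Chi-squared test". The effect measure is the risk ratio (RR).

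**Adjusted model.** The same paragraph continues: "A secondary binomial regression with log link will also be employed". This compares the arms "after adjusting for baseline variables identified as significant using a stepwise selection procedure". It then says that the analysis takes account of site, and that "this will be done by adjusting the model using a dummy variable for site".

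**Reporting.** Table 5 labels the chi-squared result unadjusted and the regression result adjusted. It gives an RR, confidence interval and p-value of each kind for the primary outcome and six secondary abstinence outcomes.

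**Economic analysis.** Under Basecase analysis the covariates are fixed in advance. The QALY difference "will be controlled for utility value at baseline, age, sex, study site, entitlement of free prescriptions, ethnicity and baseline FTCD". The cost difference uses the same list, with baseline health resource use in place of utility.

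**The concern.** Two choices in the main efficacy analysis are weaker than they need to be.

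1. Stratified randomisation balances the arms within site. A test that ignores site still counts between-site variation as error, so it claims slightly less precision than the design delivers. A chi-squared test has no model to hold a dummy variable, so the sentence on site can apply only to the regression. Table 5 agrees with that reading.

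2. The only site-adjusted estimate of abstinence depends on covariates picked from the trial data. The SAP names no candidates, direction or removal rule. The general 5% significance level might serve as the entry rule, but the plan does not say so. Nor does it say whether selection is repeated for each row of Table 5. Two statisticians following the plan could report different adjusted RRs, and the covariates could change from one outcome to the next.

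At stake are a little power in the primary test and the reproducibility of the adjusted column of Table 5.

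**Working it through.** **1. The plan's own figure.** Inputs from Sample size determination: 443 per arm, 10% against 17%, two-sided 5%.

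z = [0.07 × √443 − 1.96 × √(2 × 0.135 × 0.865)] / √(0.10 × 0.90 + 0.17 × 0.83) = (1.4733 − 0.9472) / 0.4807 = 1.094, so power = 86.3%.

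This reproduces the stated 86%, and it is the power of the unstratified test.

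**2. Why ignoring site is conservative.** With balance within equal-sized sites, the crude test uses variance p̄(1 − p̄). The variance that applies is smaller by V, the mean of (pᵢ − p̄)². The SAP gives no site-specific rates, so these are assumed:

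- 8/10/12%: V = 0.00027; 0.00027 / 0.09 = 0.3%.
- 5/10/15%: V = 0.00167; 0.00167 / 0.09 = 1.9%.
- 5/10/20%: V = 0.00389; 0.00389 / 0.1031 = 3.8%.
- 2/8/20%: V = 0.0056; 0.0056 / 0.09 = 6.2%.

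The effective critical value is 1.96 / √(1 − share). For 5/10/15% that is 1.978, a two-sided level of 4.8%. For 2/8/20% it is 2.024, a level of 4.3%.

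**3. Simulation of the primary test.** 200,000 trials per scenario, 886 participants, near-equal sites, arms balanced within site, RR 1.7 for power. The site-stratified test is Cochran-Mantel-Haenszel (CMH).

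| Assumed control rates by site | Type I error, crude / CMH | Power, crude / CMH |
|---|---|---|
| 10/10/10% | 5.1% / 5.0% | 86.7% / 86.7% |
| 7/10/13% | 5.0% / 5.0% | 86.7% / 86.9% |
| 5/10/15% | 4.8% / 4.9% | 87.0% / 87.5% |
| 5/10/10/15% (four sites) | 4.9% / 5.0% | 86.9% / 87.2% |
| 5/5/20% | 4.5% / 5.0% | 87.6% / 89.2% |
| 2/8/20% | 4.4% / 5.0% | 87.7% / 89.5% |

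The gain from stratifying runs from 0 to 89.5 − 87.7 = 1.8 points. It exceeds about half a point only in the two most uneven scenarios.

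**4. Simulation of the stepwise step.** 500 trials with no effect and 500 at RR 1.7. Site was forced in. There were 14 independent candidates, of which four were truly prognostic (log-RR −0.3, 0.2, 0.15 and 0.1 per SD). Selection was forward, with entry at p < 0.05. Poisson regression with robust standard errors stood in for the log-binomial model.

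- Covariate sets chosen: 138 different sets with no effect and 136 at RR 1.7. The commonest appeared in 13.4% and 14.0% of trials.
- Stepwise RR divided by site-only RR, 95% range: 0.93 to 1.07.
- Type I error: 3.4% site only, 3.8% stepwise, 4.4% all covariates. Simulation error is √(0.05 × 0.95 / 500), about 1 point, so these do not differ reliably.
- Power: 87.2%, 87.4% and 87.8% respectively.
- Chance that at least one pure-noise candidate enters, if they are independent: 1 − 0.95¹⁰ = 40% for ten and 1 − 0.95¹⁴ = 51% for fourteen.

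**5. Scale of the shift.** At 10% against 17% the standard error of log RR is √(0.90 / 44.3 + 0.83 / 75.3) = 0.177. A 7% shift is ln(1.07) = 0.068, so 0.068 / 0.177 = 0.38 of a standard error. Part of any shift is legitimate correction of chance imbalance, which a fixed list would also make. The simulation does not separate that part from the noise of selection.

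**The case against.** The strongest defence is that nothing here is broken. The crude test matches the test behind the 86% power figure. Site is not overlooked: it is forced into the regression, and Table 5 commits in advance to unadjusted and adjusted results side by side. The final analysis is to be done blind to allocation, which limits any deliberate choice of a favourable model. The SAP also records no change from the protocol's planned analysis, so a new primary test would be a late departure. The economic covariate list was written for another purpose, and six ethnicity categories could give sparse cells.

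Much of this stands, and it bounds the point. Blinding, however, does not make a data-driven covariate set stable or reproducible. The remaining practical objections are met by keeping the crude test as supportive, collapsing ethnicity and naming a fallback model.

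Three stronger readings are tempting but not supported:

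- *The primary test is invalid.* It errs, if at all, on the conservative side.
- *The adjusted confidence interval and p-value are invalid because the model was selected.* The simulation in the working shows no type I inflation. A second one, of 600 null trials with 12 assumed candidates, gave 5.0% for the unadjusted, stepwise and fixed models alike.
- *A single dummy cannot code several sites.* The phrase is ordinary shorthand for indicator coding. The four services in the Summary and three places in Table 1 need not conflict, since one place may hold more than one service.

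**Conclusion.** The point holds as a worthwhile improvement to a stated method, not as a flaw that threatens the trial's conclusion. The primary abstinence test omits the only stratification factor. The only site-adjusted abstinence analysis takes its other covariates from an incompletely specified stepwise procedure. The economic analysis does adjust for site with a fixed list, so the criticism is confined to the abstinence outcomes.

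For the primary test, the size is a type I error of about 4.4% to 5.1% and a power loss of 0 to about 2 points. For the adjusted RR, it is an unstable covariate set and movement of roughly -7% to +7% relative to a site-only model, without alpha inflation. These figures rest on assumed site rates, near-equal site sizes and assumed independent covariates. None of these is in the SAP, and correlated real covariates could behave differently. That the primary test is unstratified and the covariates are not fixed in advance rests on the text alone.

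**What to change.** 1. Make the primary analysis site-stratified: either a CMH test with its stratified RR, or an RR model with indicators for the sites as used in the randomisation. Keep the crude chi-squared test as supportive, and say plainly which analysis the sentence on site governs.
2. Replace stepwise selection with a fixed list for every abstinence outcome. The one under Basecase analysis serves, without its outcome-specific baseline term: site, age, sex, free-prescription entitlement, ethnicity and baseline FTCD.
3. Collapse ethnicity if cells are sparse. At 10% against 17% about 44.3 + 75.3 = 119.6 events are expected. With three sites and six ethnicity categories the model has 1 + 2 + 1 + 1 + 1 + 5 + 1 = 12 terms, or 119.6 / 12 = 10 events per term. With two ethnicity categories it has 8 terms, or 15 events per term.
4. Name Poisson regression with robust standard errors as the fallback if the log-binomial model does not converge.

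The variables are already collected and N stays at 886. The downside is a departure from the chi-squared test now named as primary. It should be decided by blinded members of the team and recorded, with its date, as a change made before unblinding.
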